Study procedures	
Refer to the Schedule of Assessments and Study Procedures (Section 6)

Statistics	
Primary Objective: To evaluate the proportion of patients with undetectable HCV RNA at 12 weeks post end of treatment (SVR12) following elbasvir/grazoprevir therapy among PWID with recent injecting drug use or receiving OST and chronic HCV genotype 1 or 4 infection and evaluate demographic and clinical predictors of non-response.
 
Assuming an overall SVR of 90% (135 of 150), the 95% confidence interval around this estimate will be 84.0% to 94.3%. This study will have robust power to examine the effect of treatment setting on SVR: e.g. 80% power to detect an odds ratio of 0.39 or 2.59 or more extreme (with alpha=0.05)

for a variable that is 50% prevalent.

Secondary Objective: Estimate incidence and predictors of HCV reinfection after successful elbasvir/grazoprevir.

Schedule of Assessments

Assessment / Procedure	Screen	Baseline	W4	Safety	Study Treatment (weeks)	Follow-up (weeks)							
						24	36	48	60	84	108	132	156
Study weeks	-6 to 0	0	4	8	12 (ETR)	24 (SVR12)	36 (FU1)	48 (FU2)	60 (FU3)	84 (FU4)	108 (FU5)	132 (FU6)	156 (FU7)
Study Days	-42 to 0	0	28	56	84	168	252	336	420	588	756	924	1092
Visit Window (Days)			+/- 7	+/- 7	+/- 14	+/- 14	+/- 14	+/- 14	+/- 14	+/- 14	+/- 14	+/- 14	+/- 14
Informed consent, medical history	x												
Vital signs & physical measurements	x	x											
HCV-RNA testing (Local Laboratory)	x ^a		x ^a		x	x	x ^d						
HCV genotyping (Local Laboratory)	x												
Behavioural survey	x												
Abbreviated behavioural survey		x			x	x	x	x	x	x	x	x	x
Adherence survey and pill count			x	x	x								
Health outcomes survey (EQ-5D)	x				x	x							
Liver function tests/ Full blood count/ Biochemistry	x	x		x ^c	x	x							
HIV & HBV serology	x												
Fibroscan	x												
Pregnancy Test	x	x	x	x	x	x ^f							
Serious Adverse Events		x	x	x	x	x ^e							
Concomitant medication	x	x			x								
Research Sample (10 mL EDTA plasma and Whole Blood)	x ^b	x ^b	x	x	x	x	x	x	x	x	x	x	x
HCV sequencing/resistance testing (tested at Central lab using 10ml of research sample)						x ^g							
Finger-stick point-of-care HCV RNA testing (sub-study sites only)	x	x	x			x	x	x	x	x	x	x	x

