^a must be quantitative HCV RNA, ^b 4ml whole Blood and 20mL EDTA at Screening and Baseline only, ^c ALT only, ^d as per standard of care, ^e to week 16 only, ^f at 14 days post end of treatment (home test allowed) ^g To evaluate the prevalence of resistance associated substitutions and for relapse or reinfection as needed

1. Background and rationale

People who inject drugs (PWID) account for the majority of new (80%) and existing (60%) cases of HCV in high-income countries^{1, 2}. Development of chronic HCV infection may lead to progressive hepatic fibrosis, cirrhosis, and complications of liver failure or hepatocellular carcinoma³. The ageing cohort of PWID populations means that liver disease-related mortality is increasing⁴⁻⁷. However, treatment can attenuate HCV-related disease consequences, including all-cause mortality⁸. HCV transmission also continues to occur among PWID⁹. Estimated HCV incidence among PWID ranges from 5-45% per annum¹⁰. The risk of HCV infection is highest among recent initiates into injecting drug use. Harm reduction strategies, such as needle syringe programs (NSP) and opioid substitution treatment (OST) have been successful for HIV prevention among PWID, but have been less effective for HCV prevention¹¹⁻¹⁵. In many countries, low coverage of NSP and OST further hinders HCV prevention efforts¹⁶. Given that HCV transmission continues to occur among PWID and there is no HCV vaccine, strategies to achieve HCV elimination among PWID must be explored.

Data from mathematical modelling suggests that substantial reductions in HCV prevalence and incidence could be achieved among PWID with modest increases in treatment uptake with interferon-free HCV regimens¹⁷. Given the potential prevention benefits, HCV treatment among PWID is also cost-effective^{18, 19}. In fact, combining interferon-free HCV therapies with high coverage OST and NSP may lead to even greater reductions in HCV prevalence²⁰. As such, combination prevention strategies including “HCV Treatment as Prevention”, OST and NSP are critical for achieving reductions in HCV prevalence/transmission to very low levels¹⁸. Targeted treatment to those at risk of transmission could be used as an HCV “Treatment as Prevention” strategy to reduce onward transmission.

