6.1 Visits and Procedures

The following assessments must be conducted at study visits as per the schedule of assessments:

Vital signs & physical measurements	Sitting systolic and diastolic blood pressure, heart rate, body weight ^a , height ^a
Fibroscan	Within 12 months prior to screening
Biochemistry	Creatinine, glucose, sodium, chloride, and potassium
Liver Function Tests	ALT, AST, GGT, total bilirubin, albumin, alkaline phosphatase, total protein
Full Blood Count	Haemoglobin, haematocrit, White Blood Cells, platelets, neutrophils
HCV RNA	Must be quantitative at Screening (within 12 weeks prior to Screening) and Week 4
HCV Genotype	Within 12 weeks prior to screening
HBV Serology	Anti-HBc, HBsAg and Anti-HBs testing (within 6 months prior to Screening)
HIV Serology	HIV antibody (within 6 months prior to Screening)
HCG Pregnancy Test	For women of childbearing potential, a negative urine (or serum) HCG test at screening, baseline, weeks 4, 8, week 12 (ETR) and week 14 (home test allowed at week 14)
Questionnaires	Behavioural survey, abbreviated behavioural survey, adherence questionnaire and EQ-5D
Finger-stick point-of-care HCV RNA testing (POC)	At sub-study sites only

^a at screening only

The following assessments and procedures must be performed at each visit as specified below:

Initial screening period (Week -6 to Week 0)

- Informed consent
- Medical history
- Vital signs and physical measurements
- Quantitative HCV RNA and genotype (Local Laboratory)
- LFTs, FBC and biochemistry
- HIV & HBV serology
- Fibroscan
- Pregnancy test (females of child bearing potential only)
- Concomitant medication
- Study questionnaires (Behavioural and EQ-5D)
- Research specimen collection (EDTA plasma & whole blood)
- Finger-stick point-of-care HCV RNA testing (Sub-study sites only)

Baseline visit (Week 0)

- Vital signs and physical measurements
- LFTs, FBC and biochemistry
- Pregnancy test (females of child bearing potential only)
- Serious Adverse Events
- Concomitant medication
- Study questionnaires (Abbreviated Behavioural)
- Research specimen collection (EDTA plasma & whole blood)
- Finger-stick point-of-care HCV RNA testing (Sub-study sites only)

On-Treatment Visits

Week 4 (+/- 7 days)

- Quantitative HCV RNA (Local laboratory)
- Pregnancy test (females of child bearing potential only)
- Serious Adverse Events
- Research specimen collection (EDTA plasma)
- Study questionnaire (Adherence)
- Finger-stick point-of-care HCV RNA testing (Sub-study sites only)

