
Week 8 (+/- 7 days)

- LFTs – ALT only
- Pregnancy test (females of child bearing potential only)
- Serious Adverse Events
- Research specimen collection (EDTA plasma)
- Study questionnaire (Adherence)

End of Treatment (ETR) - Week 12 (+/-14 days)

- Qualitative HCV RNA (where available, otherwise quantitative), (Local laboratory)
- LFTs, FBC and biochemistry
- Pregnancy test (females of child bearing potential only)
- Serious Adverse Events
- Concomitant medication
- Study questionnaires (Abbreviated Behavioural, Adherence, and EQ-5D)
- Research specimen collection (EDTA plasma)

Post Treatment Follow-up Visits

Post Treatment Week 12 (SVR12) - Week 24 (+/- 14 days)

- Qualitative HCV RNA (Where available, otherwise quantitative) (Local laboratory)
- LFTs, FBC and biochemistry
- Pregnancy test (females of child bearing potential only) (at 14 days post end of treatment – home test allowed)
- Serious Adverse Events (up to week 16 (SVR4) only)
- Study questionnaires (Abbreviated Behavioural and EQ-5D)
- Research specimen collection (EDTA plasma)
- Finger-stick point-of-care HCV RNA testing (Sub-study sites only)

Post Treatment Weeks 36 (FU1), 48 (FU2), 60 (FU3), 84 (FU4), 108 (FU5), 132 (FU6) and 156 (FU7) (+/- 14 days)

- Qualitative HCV RNA (Where available, otherwise quantitative) (Local laboratory)
- Study questionnaires (Abbreviated Behavioural)
- Research specimen collection (EDTA plasma)
- Finger-stick point-of-care HCV RNA testing (Sub-study sites only)

If a patient has suspected viral relapse or HCV reinfection HCV RNA sequencing will be performed. No additional sample is required.

Monitoring of HBV reactivation

At screening, all patients will be tested for evidence of current (Hepatitis B surface antigen positive) and prior (anti-Hepatitis B core antibody positive) HBV infection before initiation of treatment. Patients with current HBV infection will be excluded. Patients with evidence of prior HBV infection only will be enrolled.

Patients with evidence of prior HBV infection will be monitored for HBV reactivation and hepatitis flare during HCV treatment and post-treatment follow-up. LFTs will be performed 4-weekly during treatment. In the setting of a clinically significant ALT elevation or symptoms and signs of acute hepatitis, HBV DNA testing will be performed to assess for reactivation. Appropriate management for HBV infection will be initiated by the site investigator as clinically indicated.

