Hypothesis 2.1: The incidence of HCV reinfection following successful elbasvir/grazoprevir therapy will be <8 per 100 p-yrs among people with recent injecting drug use or receiving OST.

Hypothesis 2.2: HCV reinfection will be associated with ongoing \geq daily injecting drug use, and needle and syringe borrowing. OST and high-coverage access to needle and syringes will be associated with reduced HCV reinfection.

Outcome: Incidence of HCV reinfection following successful elbasvir/grazoprevir therapy.

Statistical analysis: Rates of HCV reinfection will be calculated using person-time of observation. The estimated date of reinfection will be calculated as the midpoint between the dates of the last undetectable HCV RNA test and the first detectable HCV RNA test at the time of HCV reinfection. Time at risk will commence at the date of undetectable HCV RNA at end of treatment and end at the first of estimated date of re-infection, death, loss-to-follow up or end of study. Confidence intervals for rates will be calculated using a Poisson distribution.

Cox proportional hazards analyses (or other appropriate regression models) will be used to estimate crude and adjusted hazard ratios and corresponding 95%CI to evaluate factors associated with reinfection. Factors hypothesised to be associated with reinfection include demographic factors (age, sex), injecting behaviours (current injecting drug use, daily injecting, type of drug injected, injecting equipment borrowing), use of needle and syringe programs, and opioid substitution treatment with time-updated co-variables.

Sample Size: Overall, based on previous reports of HCV reinfection among current PWID³², and assuming loss to follow-up is 20% per year, it is estimated that the overall reinfection rate will be 8/100 p-yrs (95%CI 5.3, 11.4; 337 p-yrs of follow-up; 27 reinfections). Overall (135 with successful therapy, 27 reinfections), we will have 80% power to detect a hazards ratio (HR) of 2.94 or greater (with alpha=0.05) for a variable 50% prevalent (e.g. ongoing injecting drug use).

Collateral research

Evaluation of HCV phylogenetics

All participants enrolled in this study with available plasma samples at screening or baseline (HCV RNA detectable) will be sequenced for HCV RNA for evaluation of HCV phylogenetics.

Evaluation of HCV re-infection

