All participants with an ETR will be followed for up to three years post-ETR to assess HCV reinfection. Participants with viral recurrence (detectable HCV RNA following HCV virological suppression, reinfection rate: 8/100 person years, estimated n=27 x 2 samples=54 total samples) will be identified and available follow-up plasma samples assessed for re-infection.

The sensitivity and specificity of the Xpert® HCV Viral Load point-of-care test for detection of HCV RNA in plasma samples collected via venepuncture and capillary whole-blood samples collected by finger-stick will be assessed using both detectable and quantifiable thresholds (limit of quantification >10 IU/mL) for each assay compared to the local laboratory HCV RNA assay in plasma as the gold standard. A Bland-Altman difference plot will be generated to assess bias and agreement measurements, including limits of agreement, between the quantification of HCV by Xpert® HCV Viral Load both sample types, compared to the local laboratory HCV RNA assay in plasma.

11. Data Safety and Monitoring Board (DSMB).

A Data Safety Monitoring Board will not be used for this study as the drug is being prescribed and supplied according to indication via the PBS.

The study Medical Monitor, A/[name] will oversee all serious adverse events for DARLO-C. A/[name] is independent of the study project management team and Protocol Steering Committee. A/[name] is also a clinician at St Vincent's Hospital which is one of the recruiting sites. Should an SAE occur in a patient under A/[name] care the project team will seek an independent review of the SAE from a suitably qualified independent Infectious Diseases Specialist or Hepatologist.

12. Data collection, source documents and record retention

The Principal Investigator and the institution where the study will be conducted will permit study-related monitoring, audits, ethics committee review and regulatory inspection providing direct access to source documents.

Data will be collected on study specific electronic or paper copy case record forms. The Principal Investigator is responsible for ensuring the data collected are complete, accurate and recorded in a timely manner.

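### Reinfection person-time runs past the last HCV RNA result, and the Schedule and Section 6.1 disagree on whether that test is required after Week 24

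*Combined protocol and SAP*

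**What the plan says.** **Schedule of Assessments.** The row "HCV-RNA testing (Local Laboratory" has plain marks at Weeks 12 and 24, then a mark with footnote d, which reads "as per standard of care". In the extracted table this mark sits under Week 36 and the later cells are blank. A merged cell covering Weeks 36 to 156 is likely, and nothing below relies on the blanks.

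**Section 6.1.** The visit lists open with "The following assessments and procedures must be performed at each visit as specified below". The block "Post Treatment Weeks 36 (FU1), 48 (FU2), 60 (FU3), 84 (FU4), 108 (FU5), 132 (FU6) and 156 (FU7) (+/- 14 days" includes a local HCV RNA test with no standard-of-care condition.

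**Other sources of HCV RNA data.** Research EDTA plasma is scheduled without qualification at every visit to Week 156. Section 9.1 gives HCV RNA testing as one of its purposes, says it serves the study endpoints, and says viral load will be measured. It does not say at which visits or when. Sub-study sites also run finger-stick HCV RNA at each visit from Week 24.

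**Section 10.** A reinfection is dated at the midpoint between the last undetectable and first detectable result. Time at risk starts at the undetectable end-of-treatment result and will "end at the first of estimated date of re-infection, death, loss-to-follow up or end of study". The date of loss to follow-up is not defined. Under collateral research, participants with viral recurrence "will be identified and available follow-up plasma samples assessed for re-infection". The secondary hypothesis is a rate below 8 per 100 person-years.

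**The concern.** A reinfection can be counted only if an HCV RNA test finds it, so the numerator covers time up to each participant's last result. The denominator, as written, goes on to loss or end of study. Any time between the two is counted as free of reinfection although nobody looked. This lowers the rate, in the direction of the study's own hypothesis.

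How much untested time there is depends on how often HCV RNA is measured after Week 24, and on that the Schedule and Section 6.1 conflict. A site working from the Schedule could omit tests that a site working from Section 6.1 would do. The stored plasma could fill the gap, but the plan does not commit to assaying it at every follow-up visit. It also does not say whether the local, central or point-of-care result is the one that dates a reinfection.

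**Working it through.** **1. The plan's own figures.** Section 10 gives 27 reinfections in 337 person-years: 100 × 27/337 = 8.01 per 100. The power statement also reproduces. For a hazard ratio of 2.94, a 50% prevalent covariate, 80% power and two-sided alpha 0.05 (the side is assumed), Schoenfeld's formula gives (1.960 + 0.842)² / (0.25 × (ln 2.94)²) = 7.85 / (0.25 × 1.163) = 27 events. None of these figures is disputed.

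**2. The mechanism.** The rate is D / (time to midpoint, summed over the D reinfected, plus U summed over everyone else).
- Plan's rule: U ends at loss to follow-up, death or end of study.
- Alternative: U ends at the last HCV RNA result.

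As an illustration with assumed dates, take a participant undetectable at Week 48 and lost at Week 80, before the Week 84 visit. The plan's rule adds 80 − 48 = 32 weeks, or 32/52 = 0.62 years, in which no reinfection could have been found. If the Week 48 visit was attended but not tested and the last result was at Week 36, the untested time is 80 − 36 = 44 weeks, or 0.85 years.

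**3. The size, by simulation.**
- From the documents: true rate 0.08 per year; loss of 20% per year, taken as a constant hazard of −ln(0.8) = 0.223 per year; tests at study Weeks 24, 36, 48, 60, 84, 108, 132 and 156, which are 12 to 144 weeks after treatment; midpoint dating.
- Assumed: the share of attended FU1–FU7 visits with an HCV RNA result; the Week 24 test always done if attended; spontaneous clearance in 0% or 25% of reinfections, six months after infection; under the plan's rule, person-time running to the actual date of loss.

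Estimated rate per 100 person-years when the true rate is 8 (ranges span 25% to 0% clearance):

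| Share of FU1–FU7 visits tested | Plan's rule | Ending at last HCV RNA result |
|---|---|---|
| 100% | about 7.7 | about 8.0 |
| 80–90% | 7.2–7.6 | 7.8–8.0 |
| 50% | 5.9–6.4 | 7.5–8.0 |
| 30% | 4.6–5.1 | 7.3–8.0 |

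With full testing the shortfall is 8.0 − 7.7 = 0.3, or about 4%. At 50% tested it is 1.6 to 2.1, or 20% to 26%. Ending person-time at the last result removes it entirely when no infection clears. What remains with 25% clearance is infections that came and went between tests.

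**4. Precision.** Changing the person-time rule does not bring back missed events. If 90%, 75% or 50% of the 27 reinfections were detected (assumed shares), the events would be 24.3, 20.3 and 13.5, and Schoenfeld power at a hazard ratio of 2.94 would be 76%, 68% and 51%. Shares detected are not shares of visits tested, because a persistent infection missed at one visit is found at the next test.

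**The case against.** The strongest reply is that Section 9.1 already provides for the endpoint: plasma is drawn at every visit, is meant for HCV RNA testing and endpoint work, and will have viral load measured. Sub-study sites add point-of-care results at each follow-up visit. Footnote d may also be only a label, since Section 9.1 elsewhere equates standard of care with the local laboratory test. All of this has force. A reader might infer that reinfection will be detected only where clinics choose to test, and the documents do not support that. What stands is narrower: the two passages differ, and no sentence commits to an assay at every follow-up visit.

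The sentence on recurrence in Section 10 might be read as proof that stored plasma is not used for screening. It is weak evidence. Its count of 27 × 2 = 54 samples looks like the workload for paired sequencing to separate reinfection from relapse, and says nothing about how positivity is first found.

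A reader might also infer that injecting would appear as a risk factor merely because known injectors are tested more. With 90% of injectors' visits and 40% of others' visits tested and no true difference, the plan's rule does give a rate ratio of 1.3–1.4, against 1.0–1.07 when person-time ends at the last result. But no passage suggests testing by injecting status, so this remains hypothetical.

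Finally, the testing shares are not in the documents and may in practice be high. If loss were dated at the last tested visit, the bias from loss would disappear. The plan does not say so.

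**Conclusion.** The point holds as a defect in the person-time rule, together with an unresolved conflict about the test that feeds it. Most of the bias comes from the rule; incomplete testing determines how large it becomes and also costs events. With near-complete testing the effect is small, about 7.7 for a true 8. It becomes material if a large share of follow-up visits yield no HCV RNA result: 5.9–6.4 at half tested and 4.6–5.1 at 30%. These figures rest on the assumed testing shares, 0–25% clearance, and person-time running to the actual loss date. The direction does not depend on the testing share: whenever person-time extends past the last result, the estimate moves toward the hypothesis of a rate below 8. The documents do not show that testing will be sparse or selective, and the plan's stated event count and power are unaffected if every follow-up visit is tested. The change should be made, because it concerns the secondary endpoint and costs little.

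**What to change.** 1. In Section 10, end person-time at the last HCV RNA result for participants without reinfection. In the scenarios above this restores 7.3–8.0.
2. Reconcile footnote d with Section 6.1. Whichever reading is kept for clinical care, state that for the reinfection endpoint every attended follow-up visit yields an HCV RNA result, from the local test or from the research plasma already collected at that visit.
3. In the same sentence, name which result (local, central or point-of-care) defines the last undetectable and first detectable test.

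The first change protects the rate; the second protects the number of events and limits what clearance can hide. The cost is a footnote, one or two sentences in Section 10, slightly fewer counted person-years, and some assays on stored plasma. No new visits or blood draws are needed.

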5.1 Dosage and administration

Elbasvir/grazoprevir is to be administered once daily with or without food. Each subject must be given instructions to maintain approximately the same daily dosing interval between study drug doses. Subjects should be instructed to swallow the study medication tablet whole. Subjects should be instructed to only remove the tablet immediately prior to dosing.

For a missed dose of study medication, subjects should be instructed to take the missed dose of study medication as soon as possible during the same day. However, no more than the daily dose of elbasvir/grazoprevir should be taken on any calendar day. Subjects should be cautioned never to double the next dose with a missed dose of study drug under any circumstances.

Participants will be required to complete a monthly adherence questionnaire and unused medication will be returned for a pill count.

Elbasvir/grazoprevir is contraindicated in patients with moderate or severe hepatic impairment (Child-Pugh B or C) due to the expected significantly increased grazoprevir plasma concentration and increased risk of alanine aminotransferase (ALT) elevations.

